Research coordinators will approach all patients at day 0 of intravenous antibiotic treatment for a pulmonary exacerbation to obtain consent, determine eligibility and to complete a Data Collection Form. If the participant is female and post-menarchal, a pregnancy test will be done at day 7 before randomization to prednisone or placebo. If the test is positive, the participant is ineligible for randomization. If the test is positive, the participant and her primary care CF physician will be informed of the result in private. Every effort will be made to keep any pregnancy test results private.

All study sites will perform pulmonary function tests at day 7 of IV antibiotic therapy for a pulmonary exacerbation as part of clinical care. If based on day 7 pulmonary function testing (± 2 days), a patient has not recovered $>90\%$ of their baseline FEV_1 % predicted (Non-Responders), they will be randomized into the placebo or prednisone treatment arm (**Figure 2 Randomization Flow Chart**). Baseline lung function will be defined as the best FEV_1 in the 6 months prior to the PEx (or in the 12 months prior to PEx if there are no measurements in the 6 months prior) (3). Patients who achieve $>90\%$ of their baseline FEV_1 % predicted at day 7 (Responders) will not be randomized to prednisone or placebo but will continue in the study as outlined below.

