Patients will be randomized to receive either oral prednisone 2 mg/kg/day (max 60 mg; rounded to the nearest 10 mg) (Table 1) divided twice daily or oral placebo twice daily for 7 days in addition to the IV antibiotics prescribed by their physician (**Randomization**). On Day 7 only, it may be necessary on some occasions when the study drug (prednisone or placebo) is not available until the late afternoon, to give the study drug as one full dose (as opposed to twice daily). The choice and duration of antibiotic therapy will be left completely to the discretion of their treating physician. Study outcome measures will be obtained for all enrolled subjects at day 0 (± 2 days) and subsequently at day 7 (± 2 days), day 14 (± 2 days) of IV antibiotic treatment and at the 1 month follow up visit (approximately 1 month after day 14), as per usual standard of care (; **Table 2 Study Design Schedule**). However, day 0 may + 3 days when impacted by a Friday or long weekend admission/IV antibiotic start time. Patients who are receiving home IV antibiotic therapy for a PEx will also be eligible as they return to clinic weekly according to standard clinical care.

During the course of their admission, for patients willing to provide samples, the following specimens will be collected for the bio-repository for future analysis. All biological samples will be labeled using the patient's study number. The patient's study number will be linked to patient identifiers only by a master list that is managed by the PI and the Research Coordinator of this study:

- Sputum for inflammatory markers— For patients who can produce sputum, we will collect a research sputum sample which will be immediately sent on ice to collaborator [name] laboratory for processing for inflammatory markers and stored for future examination of biomarkers according to the standardized protocols developed by the Therapeutic Drug Network, US CF Foundation.

- Serum for biomarkers—Blood collection for future studies will occur at the time of clinical bloodwork or if a patient chooses to provide research blood separately. A total of 8 mls of blood will be drawn in two lavender top EDTA tubes in the phlebotomy clinic, stored on site and subsequently delivered to [name] laboratory at St. Paul's Hospital (a sub-site for the study) for final processing and storage.

Randomization and distribution of drug/placebo

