Randomization (1:1) will be done through central allocation of a block-randomization schedule prepared through a computer-generated random listing. Randomization will be done by the study data analyst at the Hospital for Sick Children. The analyst will be the only member of the investigative team aware of the randomization assignment and will not be directly doing the statistical analysis. He/she will not be involved in the care of the study patients or the measurement of outcomes in the study. No other research staff nor patients nor physicians will be aware of the randomization assignment. The pharmacist at each study site will call the analyst for randomization.

Once the patient is randomized, the analyst will inform the research pharmacy at each study site and they will distribute either prednisone or placebo (lactose, packaged in #0 capsules of identical appearance) to the hospital ward or the CF clinic according to dosing Table 1. Physicians and patients will be blinded to the treatment, and placebo will be produced to look identical to the treatment drug. The microbiology lab and pulmonary function lab will also be blinded to the treatment allocation. Compliance will be measured by nurses for hospitalized patients and by asking patients to return any unused medication for patients receiving homecare IV antibiotics.

Safety monitoring

Patients who are most at risk of developing side effects secondary to corticosteroid use will be excluded based on the above exclusion criteria. Subjects will be monitored with measurements of urine glucose on day 7, day 10 (\pm 2 days) and on day 14 of antibiotic treatment while on prednisone (or placebo). If the urine glucose is $> 2+$, a serum glucose measurement will be performed. All the information will be provided to the treating physicians; they can decide at any time to withdraw their patient and request unblinding of the treatment allocation. The study will be monitored by a Data Safety Monitoring Board (DSMB) (Appendix 1.2-Data Safety Monitoring Plan).

E. Study outcomes:

Primary outcome:

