Appendix 1.2

Data Safety Monitoring Plan

Although subjects will be randomized to either oral prednisone or placebo, no investigational drug will be tested in this trial. Upon funding of the study, the study will be submitted to the Research Ethics Board (REB) at the Hospital for Sick Children and all other study sub-sites). REB comments and amendments will be distributed to all sites in order to ensure that the approved study protocol is identical at all sites.

Assessment of Risk

The assessment of risk is deemed to be **moderate** in this trial due to the known side effects of prednisone (eg. hyperglycemia, hypertension, gastrointestinal bleeding). Given that we will be treating subjects with a short course of oral prednisone (7 days), we do not expect to observe the long-term side effects noted with more prolonged steroid use (eg. growth retardation, osteopenia/avascular necrosis). Although certain subjects will receive placebo, they will still be receiving antibiotic treatment for the pulmonary exacerbation which is standard of care.

Anticipated Adverse Events and Grading Scale

In the previous study by Dovey et al. 12 CF subjects received oral prednisone (2 mg/kg/day x 5 days) and 12 subjects received placebo during treatment for a pulmonary exacerbation (13).

The most common adverse events were glucosuria, hyperglycemia and hypertension.

Hypertension was reported for 2 subjects in each arm, with one prednisone treated subject withdrawn on day 2 due to this. Glucosuria was reported among 6 subjects in the prednisone arm and 1 in the placebo arm ($p=0.03$); 2 of the subjects in the prednisone arm with glucosuria also had hyperglycemia (1 of these was withdrawn due to this). Additional adverse events included headache, restlessness, heartburn, nausea/epigastric pain, swelling, increased thirst and increased urination. There were no serious events in either treatment arm.

We therefore anticipate the most common adverse events to be hyperglycemia (random serum glucose > 200 mg/dL or 13 mmol/L)(55), glucosuria ($> 1+$ urine glucose) and hypertension (defined as the 99th percentile of blood pressure measurement according to gender, age and

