height using the NIH guidelines(56)) and will monitor for these adverse events (see below-Safety Monitoring Plan). In addition, all untoward medical occurrences, whether or not deemed causally related to study participation, will be recorded and site investigators will be asked to assess both severity and whether or not the adverse event was related to study participation. We will use the following grading scale to assess adverse events:

Adverse Event Category	Description
Mild	transient event, no treatment change, e.g. glucosuria
Moderate	treatment discontinued e.g. severe/sustained hypertension or hyperglycemia
Severe	severe: death, unexpected hospitalization

Given that subjects will be randomized at the time of hospitalization for a pulmonary exacerbation, we will monitor the time to subsequent exacerbation. If we observe a shorter time to subsequent exacerbation in one of the treatment arms, this will be reported to the DSMB.

Reporting of AEs

All adverse events will be recorded by the research coordinator and reported to the study site investigator as well as the PI ([name]), who will oversee close and continuous monitoring for safety concerns throughout the trial. All serious adverse events will be reported to Health Canada, based on the Health Canada Guidance: Adverse Drug Reactions (ADRs) Reporting Criteria. All serious and unexpected adverse events will also be reported to the REB at each study site as well the REB at the Hospital for Sick Children (as study sponsor) within 48 hours of their occurrence. Adverse events will also be reported to the Data Safety Monitoring Board (DSMB) (see below) in the form of regular reports submitted every 6 months. Serious adverse events will be reported to the DSMB within 48 hours.

Safety Monitoring Plan

Hospitalized subjects will be monitored on day 7, day 10 (+/- 2 days) and on day 14 with urine dip glucose measurements while on prednisone (or placebo). If the urine glucose is > 2+, a serum glucose measurement will be performed. All the information will be provided to the treating physicians; they can decide at any time to withdraw their patient and request unblinding of the treatment allocation. To unblind a subject, the research coordinator or physician will call the PI ([name]) at [contact] [name] or page [contact]

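### The day-14 urine glucose check is described as made on study drug, but a 7-day course from day 7 ends on day 13; the checks follow antibiotic days, not dosing days.

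*Combined protocol and SAP*

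**What the plan says.** All references are to the combined protocol and SAP.

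- **Course.** Section D (Study protocol) gives prednisone "divided twice daily or oral placebo twice daily for 7 days in addition to the IV antibiotics prescribed by their physician".
- **Day 7 is a dosing day.** The same section adds: "On Day 7 only, it may be necessary on some occasions when the study drug" arrives late in the afternoon, "to give the study drug as one full dose (as opposed to twice daily"). Table 2 has drug dispensed on day 7 and accounted for on day 14. No section states the last dosing day.
- **Start of dosing.** Randomisation depends on spirometry: "If based on day 7 pulmonary function testing (± 2 days), a patient has not recovered" more than 90% of baseline, the patient is randomised.
- **Urine glucose.** Checks fall on day 7, day 10 (± 2 days) and day 14. Safety monitoring in section D ends the list "and on day 14 of antibiotic treatment while on prednisone (or placebo"). The Safety Monitoring Plan in Appendix 1.2 repeats this for inpatients: "and on day 14 with urine dip glucose measurements while on prednisone (or placebo").
- **Blood pressure.** Appendix 1.2 and Table 2 put it on the same three days, without saying that the patient is on study drug.
- **Other monitoring.** In Appendix 1.2, the coordinator visits inpatients daily to record adverse events, home patients telephone in results and events, and diabetic patients on insulin check blood glucose daily as standard care.

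**The concern.** Seven days counted from day 7 end on day 13, so a check on day 14 cannot also be on drug at nominal timing. There are also two clocks. Checks are numbered by day of antibiotics, while dosing begins after a test that may fall anywhere from day 5 to day 9. Whether a given check is on drug therefore depends on when that patient started.

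Appendix 1.2 names hyperglycaemia, glucosuria and hypertension as the adverse events it most expects, and leaves withdrawal for hypertension or hyperglycaemia to the treating physician. The dip also controls further testing: serum glucose is called for only when the dip exceeds 2+. A dip made outside dosing may leave a rise during dosing unmeasured. The daily coordinator visit records events but schedules no glucose or blood pressure measurement.

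**Working it through.** **Inputs**

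- Course length: 7 days, two doses a day (section D).
- Nominal first dosing day: day 7 (section D, Table 2).
- Randomising spirometry: day 7 ± 2, that is days 5 to 9 (section D). I assume the first dose is given on the day of that test.
- Checks: day 7, day 10 ± 2 (days 8 to 12) and day 14 (section D, Appendix 1.2, Table 2).

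**Step 1. Try to reproduce day 14 as a day on drug.** Last dosing day = first dosing day + 7 − 1. With a first dose on day 7 this is 7 + 6 = 13. Day 14 is 14 − 13 = 1 day after it, so the description is not reproduced at nominal timing.

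**Step 2. Classify the nominal checks.**

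- Day 7 is the first dosing day. The documents do not say whether the check comes before or after the first dose.
- Day 10 is dosing day 10 − 7 + 1 = 4, on drug.
- Day 14 is the first day after the course.

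One scheduled check after day 7 is on drug.

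**Step 3. Find what would put a dose on day 14.**

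- A later start: first day + 6 ≥ 14 requires a first dose on day 8 or later.
- A half-day start: 2 × 7 = 14 divided doses beginning on the evening of day 7 give 1 dose on day 7, 12 on days 8 to 13, and the last on the morning of day 14. The allowance for one full dose on day 7 avoids this where it is used, because the whole of that day's dose is then given.

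**Step 4. Apply the ± 2 day window to the start.**

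| First dose (day) | Last dosing day | 14 − last dosing day | Day-14 check | Day-10 window (days 8–12) |
|---|---|---|---|---|
| 5 | 11 | 3 | after the course | day 12 is after the course |
| 6 | 12 | 2 | after the course | all on drug |
| 7 | 13 | 1 | after the course | all on drug |
| 8 | 14 | 0 | last dosing day | all on drug |
| 9 | 15 | −1 | on drug | on drug from day 9 |

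**Step 5. Sensitivity.** The safety text gives no window for the day-14 check. If it moves with the day-14 outcome visit (± 2, days 12 to 16), the number of on-drug check days for starts on days 5 to 9 is 0, 1, 2, 3 and 4. That is 10 of the 5 × 5 = 25 start-and-check pairs on drug and 15 off. This counts combinations and is not a probability, since the documents give no distribution of start days.

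**The case against.** The strongest reply is that this is a one-day looseness of wording. The last dosing day is inferred. Starts on day 8 or 9, or an evening half dose on day 7, would put a dose on day 14. At nominal timing the gap runs only from the evening of day 13 to day 14, and Table 2 already uses day 14 for drug accountability, so it works as an end-of-treatment visit. Adverse events also arrive by other routes: daily inpatient visits, telephone reports, weekly clinic returns for home patients, and daily glucose checks in insulin users. All of this stands and limits the consequence. It does not make day 14 a dosing day at nominal timing, and it does not align the two clocks.

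A reader might go further than the documents allow on several points:

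- **Blood pressure.** One might infer that it too is described as on drug. Only urine glucose is; for blood pressure the point is timing alone.
- **A check before any drug.** One might place a day-10 check on day 8, ahead of a day-9 start. Table 2 limits these checks to randomised patients, and a patient randomised on day 9 is not due one on day 8.
- **A course with no on-drug check after its first day.** For a day-5 start with the day-10 check made on day 12, this also requires the day-7 check to move to day 5 with the spirometry. Made on day 7, it falls on the third dosing day.
- **The earlier prednisone trial.** Appendix 1.2 reports hypertension there, "with one prednisone treated subject withdrawn on day 2 due to this". That may bear on how early to check, which is a clinical matter. It says nothing about whether day 14 is on drug.

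**Conclusion.** The contradiction is real at nominal timing: the course covers days 7 to 13, day 14 is the first day after it, and day 10 is the only scheduled check after day 7 that is on drug. This rests on a first dose on day 7 and seven calendar days of dosing. Across the permitted starts, day 14 is off drug for starts on days 5, 6 and 7 and on drug for starts on days 8 and 9. A day-10 check made on day 12 is off drug for a day-5 start.

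The consequence is a modest loss of on-drug detection of glucosuria, hyperglycaemia and hypertension. I put no figure on it: the documents do not say how often an affected patient would test positive or how quickly the effects fade after the last dose.

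A reader might also infer that the comparison of adverse events between arms (secondary outcome vi) is biased towards no difference. The documents do not support that. Outcome vi counts adverse events from every route, and no planned analysis classifies the checks as on-treatment. The primary outcome is not affected by this point. It should be corrected, mainly because the correction is cheap.

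**What to change.** Reconcile section D (dosing and Safety monitoring), the Safety Monitoring Plan in Appendix 1.2, and Table 2:

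1. State the first and last dosing days, including what happens when the first dose is not on day 7.
2. Define the checks meant to be on drug relative to dosing instead of the antibiotic day. The clinical team should set the timing and windows.
3. Describe any check kept at day 14 as end-of-course. Nothing here argues against having one.
4. Say explicitly whether the blood pressure checks are also meant to be on drug.
5. Record for each check whether it was made before, during or after dosing, and report safety findings with that label.

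The cost is protocol wording and one derived variable; the number of checks need not rise. The downside is that some checks may no longer coincide with the day-14 visit, although Appendix 1.2 already provides for urine and blood pressure checks at home.

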The proportion of subjects who achieve >90% of their baseline FEV₁ % predicted at day 14 of IV antibiotic treatment for a PEx in each treatment arm. Recovery of lung function will be defined as previously as an FEV₁ of >90% of baseline FEV₁ at day 14 of antibiotic therapy (3). Baseline lung function will be defined as the best FEV₁ in the 6 months prior to the PEx (or in the 12 months prior to PEx if there are no measurements in the 6 months prior). Lung function measurements will be performed according to American Thoracic Society criteria (42) and absolute values will be converted to percent predicted using the Global Lung Function Initiative-2012 reference equation (43).

Secondary outcomes:

i) The proportion of subjects who achieve >90% of their baseline FEV₁ % predicted at the 1 month follow up visit after the PEx in each treatment arm.

Patients are typically seen in CF clinic 1 month following discharge from hospital for a PEx and pulmonary function tests are done at every CF clinic visit as part of standard clinical care. Lung function recovery will be defined as per the Primary Outcome.

ii) The absolute change in pulmonary function tests, including forced expiratory volume in 1 second (FEV₁), forced vital capacity (FVC) and maximal mid-expiratory flow rate (FEF₂₅₋₇₅), measured at day 7, day 14 of IV antibiotic treatment and the 1 month visit in each treatment arm.

iii) The change in the cumulative score on a quality of life questionnaire measured by the CFQ-R and the CFRSD at day 0, day 7, day 14 of IV antibiotic treatment and the 1 month follow up visit in each treatment arm.

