Subjects will be monitored for adverse events during hospitalization by the research coordinator and will be instructed to call the research coordinator with reports of adverse events once discharged. Adverse events will also be assessed at the 1 month follow up visit. Assessment of adverse events will include any mild events (transient event, no treatment change, e.g. cough), moderate events (treatment discontinued, e.g. hypertension, hyperglycemia) and severe events (gastrointestinal bleed, hospitalization or death). In the 1 year follow up, new infections with *P. aeruginosa*, *M. abscessus* or *B. cepacia* complex will be recorded in each group. Adverse events will be reported to the Research Ethics Board of each study site and to the study's Data Safety Monitoring Board (DSMB). Withdrawals from the study and the reason for it will also be recorded as an outcome measure.

vii) The change in the measurement of sputum (neutrophil count, neutrophil elastase and IL-8 levels) and serum (including neutrophil count and hsCRP) inflammatory markers measured at day 0, day 7, day 14 of IV antibiotic treatment and the 1 month follow up visit in each treatment arm.

The anti-inflammatory effects of steroid therapy will be examined in both the lung and serum. Sputum will be collected at all study sites and immediately shipped on ice to collaborator [name] laboratory for processing as previously described according the standardized protocols developed by the Therapeutic Drug Network, US CF Foundation (48). Serum samples will also be collected at these time points for neutrophil count and CRP measurements through the hospital laboratory as part of clinical care and an aliquot will be banked for future serum biomarker studies at each study site (49-50).

F. Sample size calculation

To calculate the sample size for the primary outcome, we did an analysis using the Toronto CF Database of all the PExs treated with IV antibiotics from 1997-2012 at the Hospital for Sick Children and St Michael's Hospital (almost 3,000 PEx). When examining PExs for which all

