When target sample size is reached, the study statistician (who will not be involved in the conduct of the study) will unblind the treatment allocation (identify who is in group A vs B but not identify the groups themselves as active drug or placebo) and estimate the treatment effect between the two groups based on the primary outcome (intention-to-treat). If there is a statistically significant treatment effect ($p<0.05$), the study statistician will do the following statistical analyses. For the primary outcome we will compare the proportion of randomized patients that responded at day 14 of therapy in the placebo arm compared with the treatment arm using a two sample test for proportions. We will perform intent-to-treat analysis according to the treatment arm subjects were randomized to. We will also perform a per-protocol analysis based on subjects who completed the 7 days of prednisone or placebo as per protocol. The same analysis will be performed for the proportion responding to therapy at 1 month. Logistic regression analysis will then be performed to adjust for potential confounders, such as age, gender, *Pseudomonas aeruginosa* or methicillin-resistant *Staphylococcus aureus* (MRSA) infection and lower FEV₁, as these factors have been associated with failure to recover lung function after an exacerbation (3, 25). For the additional secondary outcomes, absolute change in pulmonary function tests, length of hospitalizations and change in sputum measurements,

we will use parametric (t-test), or non-parametric (Mann-Whitney) two sample comparison test. Linear regression analysis will be then performed to adjust for potential confounders, as listed above. Time to subsequent exacerbation will be compared using a Cox proportional hazard model. Potential confounders will be adjusted for in the Cox-proportional hazard model. All secondary outcomes will be analyzed both as intention-to-treat and per-protocol. All outcomes will be obtained for all subjects irrespective of whether they completed the study per protocol. In the case of missing data, we will perform the analysis on complete (complete case analysis). To determine whether diabetic patients have a different response compared to non-diabetic patients, we will perform a sensitivity analysis comparing return to baseline lung function in diabetics vs non-diabetics according to treatment group.

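### Secondary change outcomes have no stated reference time, and the day-7 value at randomisation is collected but not used as a covariate

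*Combined protocol and SAP*

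**What the plan says.** Section D (Study protocol) places randomisation at the day-7 visit, for patients who have not regained enough lung function: "If based on day 7 pulmonary function testing (± 2 days), a patient has not recovered". Study drug is dispensed at day 7 (Table 2) and given for 7 days.

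Section E gives three continuous outcomes as a change, each followed by a list of visits:

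- Outcome ii (spirometry): "measured at day 7, day 14 of IV antibiotic treatment and the 1 month visit in each treatment arm". Day 0 is not listed, although Table 2 schedules spirometry then.
- Outcome iii (questionnaires): "measured by the CFQ-R and the CFRSD at day 0, day 7, day 14 of IV antibiotic treatment", and at 1 month.
- Outcome vii (sputum and serum): "inflammatory markers measured at day 0, day 7, day 14 of IV antibiotic treatment and the 1 month follow up visit in each treatment arm".

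None of these says which visit is subtracted. The only baseline that Section E defines is the best FEV₁ in the 6 (or 12) months before the exacerbation, which serves the recovery outcomes.

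Section G assigns a test to "absolute change in pulmonary function tests, length of hospitalizations and change in sputum measurements". For these outcomes it plans a simple comparison of the arms: "we will use parametric (t-test), or non-parametric (Mann-Whitney) two sample comparison test". Linear regression follows, on the confounders listed for the primary outcome: age, gender, *P. aeruginosa* or MRSA infection, and lower FEV₁ with no time point. CFQ-R, CFRSD and serum markers are not named for any test. Missing data are handled by complete-case analysis.

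**The concern.** What happens between day 0 and day 7 precedes study drug and cannot be an effect of it. If change is taken from day 0, variation from that week and chance day-0 differences between arms enter the estimate. The day-7 value is the natural baseline and is scheduled for spirometry, both questionnaires, sputum and serum, yet no analysis is said to use it.

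The precision of the patient-reported and mechanistic comparisons is at stake. These are small: at most about 42 per arm, and probably fewer for neutrophil elastase and IL-8, because Section D collects sputum only from willing patients who can produce it. Section B itself criticises the earlier prednisone trial for having too few sputum measurements. That trial randomised on the first day of antibiotics and measured IL-8 change from day 1. Here randomisation has moved to day 7, and the wording of outcomes iii and vii does not say whether the reference moved with it.

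Under Section G the secondary analyses are run after the data have been split into groups A and B and the primary outcome tested. A reference time left open until then could be chosen with results by group in view.

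**Working it through.** **The plan's own figure.** Section F gives 42 per arm for 30% vs 60%, 80% power, 5% significance (two-sided assumed). With pooled variance:

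n = [1.96·√(2·0.45·0.55) + 0.84·√(0.3·0.7 + 0.6·0.4)]² / 0.30² = (1.379 + 0.565)² / 0.09 ≈ 42.

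It reproduces. No power is stated for any change outcome.

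**Inputs for the check.** 42 per arm is from Section F. The documents give no correlations, so all of those below are assumptions. Variances are taken as equal across visits and set to 1. Let r0 be the correlation of day 0 with day 14, and r7 that of day 7 with day 14.

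**Variance per patient of three day-14 analyses**

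- Unadjusted change from day 0: 2(1 − r0)
- Unadjusted change from day 7: 2(1 − r7)
- Day-14 value adjusted for the day-7 value: 1 − r7²

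**Adjusted day-14 value against unadjusted change from day 0**

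| Assumption | Ratio | Variance saved |
|---|---|---|
| All correlations 0.3 | 0.91/1.40 = 0.65 | 35% |
| All 0.5 | 0.75/1.00 = 0.75 | 25% |
| All 0.7 | 0.51/0.60 = 0.85 | 15% |
| All 0.9 | 0.19/0.20 = 0.95 | 5% |
| Autoregressive (r0 = r7²), any r7 | (1 − r7²)/[2(1 − r7²)] = 0.50 | 50% |
| r0 = 0.4, r7 = 0.6 | 0.64/1.20 = 0.53 | 47% |
| r0 = 0.5, r7 = 0.7 | 0.51/1.00 = 0.51 | 49% |
| r0 = 0.6, r7 = 0.8 | 0.36/0.80 = 0.45 | 55% |

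The range is 5-55% in variance. In standard error that is √0.95 = 0.97 to √0.45 = 0.67, or about 3-33% smaller.

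**Against unadjusted change from day 7.** The ratio is (1 − r7²)/[2(1 − r7)] = (1 + r7)/2. It runs from 0.65 at r7 = 0.3 to 0.95 at r7 = 0.9, a saving of 35% down to 5%. The 1-month value follows the same formula with its own correlation with day 7.

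**What this means with 42 per arm.** Detectable difference in SD units = (1.96 + 0.84)·√(2V/42), where V is the variance above. With r7 = 0.7:

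- All correlations equal: 0.474 (V = 0.60) falls to 0.437 (V = 0.51). Power for 0.5 SD rises from 84% to 89%.
- Autoregressive: 0.617 (V = 1.02) falls to 0.437. Power rises from 62% to 89%.

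**Two partial remedies.**

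- Keeping change from day 0 as the outcome and only adding the day-7 covariate gains nothing under either the equal or the autoregressive structure. The covariance of (day 14 − day 0) with day 7 is r7 minus the day 0-day 7 correlation, which is zero in both.
- Moving the reference to day 7 without adjustment gains nothing when all correlations are equal, since 2(1 − r0) = 2(1 − r7).

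**Cost of missing day-7 values.** Variance is inversely proportional to the number analysed. If complete-case analysis retains a fraction f, the ratio becomes 0.85/f when all correlations are 0.7. Losing 15% of patients would cancel the gain; with all correlations 0.9, losing 5% would. The extra parameter itself costs about 1/80, or 1%.

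**The case against.** A reader might infer that the plan measures change from day 0. The documents do not say so. Outcomes iii and vii list visit times, and outcome ii omits day 0, which fits a day-7 reference. Section D also collects the measures in all enrolled patients, including day-7 responders who are never randomised, so a day-0 visit has an ordinary purpose. This stands: the reference is unspecified, not wrong. It does not settle the matter, because both outcomes are to be reported by treatment arm and responders belong to none.

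A reader might also infer that the analysis is wholly unadjusted. It is not; regression follows the two-sample test. Lower FEV₁, if read as the day-7 value, would come close to the right covariate for FEV₁. It would not serve the questionnaires or markers.

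Selection on day-7 FEV₁ invites an argument about regression to the mean. It acts on both arms alike and does not bias a randomised comparison, though it may lower the day 7-day 14 correlation for FEV₁ and so the gain.

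Finally, the gain may be as small as 5%, and it is not free. Complete-case analysis could drop patients. The visits are "at day 0 (± 2 days) and subsequently at day 7 (± 2 days), day 14 (± 2 days) of IV antibiotic treatment", and nothing requires the day-7 questionnaire or sample to precede the first dose. Both points stand and belong in the fix.

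**Conclusion.** The point holds as one of specification and precision. The plan does not fix the reference for change, does not use the day-7 value of the outcome, and leaves three sets of outcomes (CFQ-R, CFRSD, serum markers) without a named test. The adjusted model did better in every scenario tried. The size of the gain rests entirely on assumed correlations and equal variances, and the upper end needs day 7 to be better correlated with day 14 than day 0 is.

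The documents do not support a claim of bias, nor any effect on the primary outcome or on the 84 patients planned. Nor do they support the claim that adding a day-7 covariate removes the noise at no cost: the outcome must also be the later value, or change from day 7. The change should be made before allocation by group is revealed, but the trial's main conclusion does not depend on it.

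**What to change.** In Sections E and G:

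1. Define baseline for the between-arm continuous outcomes (spirometry, CFQ-R Respiratory, CRISS, sputum and serum markers) as the last value before the first study dose, at day 7. Require the day-7 questionnaires and samples to be obtained before that dose.
2. Make the main analysis a linear model of the day-14 value, and separately the 1-month value, on treatment plus that baseline. Log-transform skewed markers. The day-0 value may be added as a further covariate.
3. Name CFQ-R, CFRSD and serum markers in Section G.
4. State how a missing day-7 value is handled, for example by simple baseline imputation, so that the patient is not dropped.
5. Report day 0-7 change descriptively only.

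The cost is wording, plus one timing rule for sites. Table 2 already schedules spirometry, questionnaires, sputum and serum at day 7, so no visit or measurement is added.
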